**Figure 1: Study design and schedule of procedures**

## 2.8 What are the proposed primary and secondary outcome measures?

The primary outcome will be the reduction of HPV DNA positivity for the target HPV vaccine types (i.e., HPVs 6, 11, 16, and 18) in multiple anatomic sites in Havrix-treated sexual partners of persons who received Gardasil. These are the combinations  $M^T F^P$  and  $M^P F^T$  in table 1. The main control group for unhindered HPV transmission will be group  $M^P F^P$  and the full protection control group is represented by the combination  $M^T F^T$ .

We will measure prevalence and incidence of HPV 6, 11, 16, and 18 infections (via DNA detection by the PCR protocol described below) in all three samples (vaginal, anal, and oral, for women, and penile, anal, and oral, for men) for the above time points among all subjects. Specimens for all three sites will be collected during all six clinic visits.

We will not exclude subjects if they are positive for HPV DNA of HPVs 6, 11, 16, and 18 because we intend to verify whether protection conferred by vaccination (both self and partner's) extends to mucosal sites that have not yet been infected by the above target types. Actually, prevalent infections at enrolment will be informative because they could be the source of a transmission event to a partner.

Reduction in HPV type concordance (for the four target types) will be the main outcome evaluable as per the above group contrasts. These comparisons will be done with due attention to the enrolment virological status of the individuals. For instance, we expect that a Havrix-treated woman who is positive for HPV 6 in the anal specimen but negative for this type in the vaginal specimen may derive benefit if her partner receives Gardasil, even if he is HPV-6 positive in the penile sample. Our assumption is that protection via vaccination is pan-mucosal, via transudation of neutralizing antibodies; this protection may mediate transmission.

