**2.10 Will health service research issues be addressed? Justify inclusion/exclusion of health economics and quality of life measures. If these measures are to be included full details should be given including power calculations.**

Health service research issues will not be directly addressed by the proposed study. However, should our trial demonstrate efficacy, its findings will be instrumental in orienting initial estimates of cost-effectiveness by our team or others. Our CIHR Team on HPV-associated diseases includes a health economist, [name], at Laval University. The results of this trial will assist in future analyses by [name]. Detailed information to inform future cost-utility analyses will be collected during the trial and will be made available to [name] (please see his letter).

**2.11 What is the proposed sample size and what is the justification for the assumptions underlying the power calculations? It is important to give the justification for the size of the difference that the trial is powered to detect. Does the sample size calculation take into account the anticipated rates of non-compliance and loss to follow-up given below?**

*Statistical power*

Empirically-based estimates of parameters for sample size calculation were obtained from our unit's molecular epidemiologic investigations of HPV infection of female university students, i.e., the McGill-Concordia cohort study and the "HPV Infection and Transmission among Couples through Heterosexual activity" (HITCH) cohort study, both funded by CIHR. The HITCH study is the same recruitment platform that will serve TRAP-HPV. Prevalence of the four Gardasil preventable HPV types (6,11,16, & 18) at enrolment was 23% and comparable between genders. The rate of acquisition of any of these types was 3.8 per 100 subject-months, which translates to approximately 40% cumulative incidence for these types in the unvaccinated HITCH population. The latter is the most empirically valid expectation for the rate of transmission events in cell  $M^{TF^P}$  in table 1. Therefore, the latter group provides the baseline comparison for the two groups in table 1 with vaccination-discordant regimens,  $M^{TF^P}$  and  $M^{PF^T}$ , whereas the concordant group with both partners receiving Gardasil ( $M^{TF^T}$ ) serves as a secondary control group where minimal transmission is expected to occur.

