We used the Bernstein and Lagakos approach to derive sample size projections for different levels of power (80% and 90%), with type one error of 0.05, and one-sided hypothesis for reductions in the above rate of transmission varying between 30% and 70%, i.e., the expected magnitude of the protective effect in the discordant vaccination groups where the partner receiving placebo is the one to be protected. We also assumed gender equivalent rates of transmission as per our findings in the HITCH study. At 80% power we would require 97 couples per group (cells in table 1) to detect a significant 40% reduction in transmission of vaccine-targeted types. A group size of 80 couples per group would be required to attain 90% power to detect a 50% reduction. The latter can be statistically detected with as little as 59 couples per group if we relax power to 80%. Evidently, larger effect sizes will have reduced requirements. There are no published empirical estimates of the expected level of transmission reduction, but our informal consultation with experts in the field, including [name], a member of our Steering Committee (see below), indicates that 40%-50% reduction in transmission is a conservative estimate for the protective effect to a partner of a vaccinated individual.

HITCH, the closest recruitment platform that TRAP-HPV will be based on, has a cumulative 16% loss to follow-up at month 12, which translates to a per-visit attrition rate of 2.7%. By applying the same expectation of losses to follow-up and using the most stringent definition of projected sample size (at 90% power and 40% effect size), we therefore propose to enroll 125 couples per group for a total of 500 couples. It is noteworthy that vaccine efficacy against HPV infection can occur with only two and even one dose. As we have observed in HITCH, the prevalence of vaccine-preventable types at enrolment is 23% and most transmission events occur early. Therefore, analyses of prevention of transmission events will begin to be informative from the second (2 months) visit and beyond.

**2.12 What is the planned recruitment rate? How will the recruitment be organized? Over what time period will recruitment take place? What evidence is there that the planned recruitment rate is achievable?**

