## **2.16 What is the proposed type of analyses?**

### *Statistical Analysis*

We hypothesize that HPV vaccination is effective in reducing the risk of HPV transmission to their sexual partners. The above plan takes advantage of the opportunity for measuring transmission events in multiple mucosal sites for multiple HPV types, over multiple clinic visits, and in both directions (i.e., male-to-female and female-to-male). We will take advantage of advanced regression methods as framework for measuring the effects expected via HPV vaccination.

In the simplest core formulation (e.g. analyzing a single HPV type and a single mucosal site), we will use the Kaplan-Meier technique to plot the cumulative probability of HPV infection in sexual partners of vaccinated versus unvaccinated individuals against follow-up time. Using the layout in table 1, this implies comparing the HPV infection histories of women in the  $M^T F^P$  and  $M^P F^P$  groups and of men in the  $M^P F^T$  and  $M^T F^P$  groups. Expectedly, protection is also likely to occur via cumulative effects observable via HPV DNA detection in multiple mucosal sites. Similar time-to-event analyses will be conducted to examine these pan-mucosal site effects.

Statistical comparisons in the HPV transmission between vaccine and control groups will be determined using the log-rank test. The Cox proportional hazard regression model will be used to estimate the effect of vaccination on transmission of HPV to sexual partners. Time to HPV infection will be defined in days as the time from study enrolment to the date of infection. Hazard ratios (HR) and their respective 95% confidence intervals will be computed. Statistical analyses will follow an intention-to-treat approach but additional regression models will examine the role of several candidate determinants in mediating transmission and the protective effects.

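### Section 2.16 gives the log-rank test and Cox model no stratum or covariate for the partner's enrolment DNA status, although section 2.8 undertakes to take enrolment infection into account

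*Combined protocol and SAP*

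**What the plan says.** Section 2.16 describes Kaplan-Meier curves of infection in partners of vaccinated and unvaccinated people. It then says "Statistical comparisons in the HPV transmission between vaccine and control groups will be determined using the log-rank test" and adds a Cox model for the effect of vaccination. Neither has a stratification factor or covariate. Further regression models are to look at factors that may mediate transmission, but those factors are not named. GEE and mixed models across types follow, and no model is labelled primary.

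Section 2.8 keeps people who are already infected in the trial, because "prevalent infections at enrolment will be informative because they could be the source of a transmission event to a partner". It also says that the group comparisons will take account of participants' infection status at enrolment.

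Sections 2.7 and 2.9 have HPV DNA measured in both partners at month 0. Section 2.3 and the randomization strategy in section 2.9 describe block randomization without stratification factors. Appendix 1 (the Gardasil 9 amendment) does commit to one stratified analysis, by prior HPV vaccination.

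Section 2.11 states that "Prevalence of the four Gardasil preventable HPV types (6,11,16, & 18) at enrolment was 23% and comparable between genders". It gives an acquisition rate of 3.8 per 100 subject-months (about 40% cumulative incidence) and uses it as the expected rate of transmission events.

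**The concern.** A placebo recipient whose partner carries a target type at enrolment is exposed from the start; one whose partner is negative is not. If that difference is strong, pooling the two kinds of couple does three things:

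- It pulls the marginal hazard ratio towards 1 and lowers the power of the log-rank test.
- It leaves the estimate open to chance imbalance in infected partners, because randomization does not balance them.
- It blurs a question that section 1.2 poses: whether a previously infected person becomes less infective once vaccinated.

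The factor is measured at enrolment, so stratifying on it does not condition on anything that happens after randomization.

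A related matter sits in section 2.11. Vaccinating a partner can prevent only infections that come from that partner, yet the planned reduction in transmission is applied to all acquisitions.

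**Working it through.** **Inputs from the documents.** "type one error of 0.05, and one-sided hypothesis" (2.11); 40% control incidence and 23% carriage (2.11); 16% loss by month 12 (2.11, 2.14); visits at 2, 4, 6, 9 and 12 months (2.7); 188 couples recruited (amendment history), so 188/4 = 47 per group if the groups are equal.

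**Assumed.** The hazard ratio k for having a carrier partner, taken as 3, 5 or 10; the vaccine hazard ratio within strata; 23% carriage, which refers to four types rather than the nine in Gardasil 9.

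**1. The plan's own figure.** "At 80% power we would require 97 couples per group (cells in table 1) to detect a significant 40% reduction". Two proportions, 40% against 24%:

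n = [1.645·√(2·0.32·0.68) + 0.842·√(0.40·0.60 + 0.24·0.76)]² / 0.16² = 105.

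For a 50% reduction the same formula gives 89 and 64, where the plan has 80 (90% power) and 59 (80% power). An exponential formula with 0.038 per month over 12 months gives 164, 137 and 99. The plan's figures are therefore not reproduced from its stated inputs. The absolute powers below are approximate; the contrast between the two tests is what matters.

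**2. Vaccine effect.** A 40% cut in a 40% risk corresponds to HR = ln(0.76)/ln(0.60) = 0.54. Hold this within both strata and solve for the baseline hazard λ:

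0.77·e^(−12λ) + 0.23·e^(−12kλ) = 0.60.

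The risk in recipients with a vaccinated partner is 0.77·(1 − e^(−12·0.54λ)) + 0.23·(1 − e^(−12·0.54kλ)), using the unrounded HR.

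| k | λ per month | Control risk, carrier partner | Risk, vaccinated partner | Overall reduction |
|---|---|---|---|---|
| 3 | 0.0317 | 68% | 24.8% | 38% |
| 5 | 0.0273 | 81% | 25.9% | 35% |
| 10 | 0.0229 | 94% | 28.3% | 29% |

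**3. Simulated power**, unstratified against stratified log-rank, detection at visits, 16% dropout, one-sided 0.05:

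| k | 97 per group | 47 per group |
|---|---|---|
| 3 | 71% v 76% | 44% v 47% |
| 5 | 66% v 75% | 40% v 47% |
| 10 | 53% v 76% | 32% v 50% |

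Repeating this with 2,000 trials per setting moved each power by at most about 2 points and put the smallest gain at 97 per group at about 4 points. The gain is thus about 4 to 23 points at 97 per group and 3 to 18 at 47.

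**4. Sensitivity.**
- Vaccine HR 0.6, 97 to 125 per group: gain about 0 at k = 1, 0 to 2 at k = 2, 2 to 4 at k = 3, 8 to 10 at k = 5, 19 to 24 at k = 10. At 47 per group: 2 to 3, 5 to 7 and 12 to 13 points for k = 3, 5 and 10.
- No vaccine effect when the partner is already a carrier, 97 per group: 43%, 38% and 30% unstratified against 41%, 38% and 30% stratified. With HR 0.6 in non-carriers the change is −1.5 to 0 points.
- No vaccine effect at all (k = 10, 97 per group): rejection 5.4% unstratified and 5.6% stratified, so stratifying leaves the error rate essentially unchanged.

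**5. Imbalance and stratum size.** The standard deviation of the between-group difference in carriage is √(2·0.23·0.77/n): 8.7 points at 47 per group and 6.0 at 97. Carrier partners number 0.23·47 ≈ 11 per group. Even if every recipient in that stratum became infected, the standard error of the log hazard ratio would be about √(1/11 + 1/11) = 0.43. Its 95% interval would span a factor of about e^(1.96·0.43) = 2.3 either way.

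**6. Acquisition against transmission (2.11).** If a fraction f of acquisitions comes from the partner, a 40% cut in transmission takes the 40% risk to 0.40·(1 − 0.4f). Two-proportion power at 97 per group is 77.5% for f = 1 (24.0%) and 59.7% for f = 0.8 (27.2%).

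**The case against.** The strongest reply is that the plan does not ignore partner infection. Section 2.8 undertakes to consider enrolment status, section 2.16 allows for further regression models, and nowhere is the log-rank test called unstratified or primary. That stands. The defect is an undertaking without a method, and unnamed covariates in additional models do not supply one.

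A second reply concerns size. A reader might infer that pooling costs the trial up to about 25 points of its planned power. The documents do not support that. They give no hazard ratio for carriage. Part of the low unstratified power at k = 10 also arises because a within-stratum HR of 0.54 is then only a 29% overall reduction. With the overall reduction held at 40% (97 per group), unstratified power is 77%, 80% and 79% for k = 3, 5 and 10, and stratified power is 81%, 88% and 96%. Stratifying still helps, but as a gain above plan. At k = 10, 94% of controls with a carrier partner become infected, which is an extreme case.

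Third, section 1.2 leaves open whether vaccination makes an infected person less infective. If it does not, stratifying gains nothing. This limits the expected benefit but creates no material harm.

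Fourth, 23% carriage over 40% incidence might be read as the share of infections that come from the partner, which would put power at 38%. That ratio is not a valid bound: it assumes that every carrier transmits and leaves out partners infected after enrolment.

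**Conclusion.** The gap is real and should be closed. Section 2.16 does not carry the undertaking in section 2.8 into its test or model, and the variable is available at no extra cost. The likely benefit runs from nothing to about 23 points of power at 97 per group and about 18 at the realised size. The upper figures need a carriage hazard ratio near 10 and an equal vaccine effect in both strata, neither of which the documents establish. The downside is at most about 2 points. The case is stronger at 47 per group, because power there is at or below about 50% throughout the table and recruitment is closed.

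The point in section 2.11 is separate. Its direction is certain if any acquisitions come from elsewhere; its size is unknown, and the fall from about 78% to 60% is only an illustration.

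**What to change.** In section 2.16, state that the log-rank test and the Cox model are stratified by the partner's enrolment DNA status for the target types (positive or negative), and that models for a single type use the partner's status for that type. Say which target types define the stratum, given the switch to Gardasil 9, and how a missing or inadequate enrolment sample is classed. Report hazard ratios by stratum with confidence intervals as descriptive results, since only about 11 partners per group would be carriers.

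In section 2.11, describe 3.8 per 100 subject-months as acquisition from any source, and show power over a stated range of partner-derived fractions.

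The cost is a few sentences, settled before the data are unblinded. No new samples or visits are needed.

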### **2.17 What is the proposed frequency of analyses?**

TRAP-HPV is an RCT that aims at obtaining empirically valid estimates of vaccine protection against transmission of preventable HPV types to partners of vaccinated individuals and to the same individuals in different mucosal sites. It is not designed to derive a therapeutic or preventive effect to assist regulatory approval of a new intended use of a vaccine. TRAP-HPV should thus be more appropriately classified as a controlled epidemiologic study whose data collection is completed in multiple visits within one year of each subject's participation. This time span is too short to be of any concern with respect to risks that may require medical intervention.

Furthermore, after 12 months there will be a crossover of vaccination regimens so that all subjects will receive the vaccine that they did not receive at enrolment. Therefore, typical design safeguards for early termination are not as important. However, to decide whether or not the trial should terminate early, the available data will be analyzed annually. An independent data safety monitoring board will review the interim analysis results. We will seek advice to McGill University's Research Ethics Board (REB) concerning the composition of this board. Members will likely be nominated by the REB, outside of our purview. The type 1 error for concluding efficacy will be controlled by the Lan-Demets spending function with O'Brien and Fleming type boundaries. The Lan-Demets method offers us flexibility to analyze the data either sporadically, or at equal intervals.

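### The men's contrast as printed uses vaccinated men as controls, and the promised type I error control is not tied to any single test

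*Combined protocol and SAP*

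**What the plan says.** - **Outcome and control (section 2.8).** The primary outcome is a reduction in HPV DNA positivity for types 6, 11, 16 and 18, at multiple sites, in placebo-assigned partners of vaccinated persons. "The main control group for unhindered HPV transmission will be group" M^P F^P. Later in the same section: "Reduction in HPV type concordance (for the four target types) will be the main outcome evaluable as per the above group contrasts".
- **Contrasts (section 2.16).** "Using the layout in table 1, this implies comparing the HPV infection histories of women in the" M^T F^P and M^P F^P groups, and those of men in the M^P F^T and M^T F^P groups.
- **Methods (section 2.16).** "Statistical comparisons in the HPV transmission between vaccine and control groups will be determined using the log-rank test". Cox regression estimates the effect: "Hazard ratios (HR) and their respective 95% confidence intervals will be computed". GEE is offered as an alternative, and mixed-effects models are also to be adopted.
- **Design error rate (section 2.11).** Sample sizes were derived "with type one error of 0.05, and one-sided hypothesis for reductions in the above rate of transmission varying between 30% and 70" per cent. On the unvaccinated 40% cumulative incidence: "The latter is the most empirically valid expectation for the rate of transmission events in cell" M^T F^P. The next sentence lists the same cell as one of the two discordant groups.
- **Interim analyses (section 2.17).** "The type 1 error for concluding efficacy will be controlled by the Lan-Demets spending function", with O'Brien-Fleming type boundaries and annual analyses. No alpha value or test statistic is given.
- **Later changes (Appendix 1).** Gardasil is replaced by Gardasil 9, anal sampling is dropped, previously vaccinated people may enter with a promise to stratify for this, and recruitment closes at 188 of 500 couples. The four-type wording of section 2.8 is unchanged.

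**The concern.** There are two linked problems.

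First, the men's contrast in section 2.16 does not isolate the partner's vaccine. Men in M^P F^T received placebo and men in M^T F^P received the HPV vaccine, so the two groups differ in their own vaccine as well as their partner's. The women's contrast in the same sentence is sound, because both groups of women received placebo.

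Second, a spending function protects one designated test statistic. Without one, the information fraction and boundary are undefined and the promise in section 2.17 cannot be checked. Spending alpha over repeated looks does nothing about error across two sexes, two outcomes or two type sets. At 188 couples the decision rule also moves power a great deal, so a choice made after seeing unblinded data would be hard to defend.

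**Working it through.** **Plan's own figures.** Section 2.17 gives no numeric boundary to reproduce. Section 2.11 gives 97, 80 and 59 couples per group. The pooled two-proportion formula at a 40% control risk and one-sided 0.05 gives 105, 89 and 64. The stated figures are matched only with inputs the plan does not give, such as a control risk near 42%. That is a separate matter; below I use the plan's 40%.

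**Men's contrast as printed.** Suppose the true partner effect is a 40% reduction and the vaccine protects the recipient by a fraction d (assumed). Risk ratio = 0.6 / (1 - d):
- d = 0: 0.6
- d = 0.4: 1.0
- d = 0.7: 2.0

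A real partner benefit could therefore appear as no effect or as harm.

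**Type I error, either-sex rule.** Let rho be the within-couple correlation of outcomes, assumed 0 to 0.5. With the comparator corrected, both sex contrasts use the M^P F^P couples, so under the null the two statistics correlate at rho/2. Error = 1 - P(Z1 < z, Z2 < z).

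| rho | each at one-sided 0.05 | each at one-sided 0.025 |
|---|---|---|
| 0 | 1 - 0.95^2 = 9.75% | 4.94% |
| 0.3 | 9.56% | 4.87% |
| 0.5 | 9.39% | 4.80% |

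With O'Brien-Fleming type spending run separately within each sex (simulated, 400,000 runs, 4 or 8 looks), the one-sided 0.05 figure stays at 9.3-9.8%. Each sex still spends its full 5%.

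**Type I error, pooled sexes without couple clustering.** With n couples per cell and null outcome variance v, the true variance of the pooled difference is v(2 + rho)/(2n); the naive variance is 2v/(2n). Error = 1 - Phi(1.645 / sqrt((2 + rho)/2)):
- rho = 0.3: 1 - Phi(1.645/1.072) = 6.3%
- rho = 0.5: 1 - Phi(1.645/1.118) = 7.1%

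**Power of each rule at closure.** Inputs: 188 couples (Appendix 1), equal cells (assumed), 16% loss (section 2.11). This gives n = 188/4 x 0.84 = 39.48 evaluable per cell. Control risk 40% and a 40% relative reduction give 24%, so v0 = 0.24 and v1 = 0.1824.
- *Pooled, clustered, one-sided 0.05:* Phi(0.16 / sqrt((v0(1 + rho) + v1)/(2n)) - 1.645). Results: 70.6% (rho 0), 64.7% (0.3), 61.2% (0.5).
- *One given direction, one-sided 0.025:* standard error sqrt(0.4224/39.48) = 0.1034, so 0.16/0.1034 = 1.547 and Phi(1.547 - 1.96) = 34%.
- *At least one direction, each at 0.025:* at rho 0, 1 - (1 - 0.340)^2 = 56.4%; 52.5% at rho 0.5.
- *Both directions, each at 0.05:* at rho 0, Phi(1.547 - 1.645)^2 = 0.461^2 = 21.2%; 25.8% at rho 0.5.

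These figures ignore interim looks, participants already positive at enrolment (23% prevalence in section 2.11) and late couples who stop at Visit 5.

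**The case against.** Much is already specified. Section 2.8 names a primary outcome, its four types and its control group. Log-rank and Cox are stated as definite, while GEE is worded as optional. Section 2.17 describes a controlled epidemiologic study aimed at estimation, not at regulatory approval. The men's comparator is probably a slip, since the other half of the sentence and section 2.8 are right. The superscripts in section 2.11 are malformed in the text available, so a PDF-reading artefact cannot be excluded there.

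Most of this stands, and it rules out several stronger readings:
- *No primary outcome or type set is designated.* Section 2.8 designates both. The defect is that it adds a competing main outcome and was not reconciled with the switch to Gardasil 9.
- *The trial's type I error is nearly doubled.* That needs an either-sex rule the plan does not state. If each sex were judged by its 95% interval, error would be 4.8-4.9%. Section 2.16 reports intervals without making them the decision rule.
- *Closure leaves almost no alpha.* Indexing spending to 500 couples would release only 0.14% at 188/500 = 0.376. No section proposes this; Appendix 1 gives feasibility as the reason for closing; and information for log-rank or Cox depends on events, not couples.

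None of it supplies the missing link. The estimation language softens the stakes but does not withdraw the promise of error control, and a slip in the text that defines the test still has to be corrected.

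**Conclusion.** The concern holds in two parts. As printed, the men's contrast cannot isolate the partner effect and contradicts section 2.8; section 2.11 appears to carry a similar mislabelled cell. Separately, the Lan-DeMets promise is attached to no single test: the sex contrasts have no pooling or multiplicity rule, a primary and a main outcome compete, and the type set was not updated.

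The size is conditional. Error is 9.4-9.75% under an either-sex rule at one-sided 0.05, and 6.3-7.1% if the sexes are pooled without clustering. Both rest on assumed within-couple correlations. The rule chosen moves power between about 21-26% (both sexes) and 61-71% (pooled), given equal cells, 16% loss and a 40% control risk. The documents do not say whether unblinding or any interim look has taken place.

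**What to change.** 1. Correct the men's comparator in section 2.16 and the baseline cell in section 2.11 to M^P F^P, in line with section 2.8.
2. Before unblinding, or dated and disclosed if unblinding has occurred, tie the boundary to one primary test on the primary outcome of section 2.8, with concordance secondary. One suitable choice is a Cox model in placebo-assigned partners (women of M^T F^P and men of M^P F^T against women and men of M^P F^P), with the partner's vaccine as exposure, stratified by sex, and variance clustered on couple. Define who is at risk from enrolment HPV status by type and site, which section 2.8 asks to be considered. Include the prior-vaccination stratification promised in Appendix 1; its coding has to be chosen, because the appendix does not give one. State the type set, the sites (genital and oral) and the sidedness.
3. If a claim per direction is wanted, state an alpha split or a both-must-succeed rule instead. The cost is power of about 34% for a given direction (52-56% for at least one) or 21-26% for both, against 61-71% pooled.
4. Record any interim looks and the alpha spent, and state that the final analysis at 188 couples spends the remainder.

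This costs SAP wording and one model, with no new data. The drawback of pooling is that the hazard ratio averages male-to-female and female-to-male transmission, so direction-specific results should be reported as secondary.
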